The study is a post market, open-label, prospective, randomized, controlled multi-center study that will evaluate DTM-SCS programming and Conventional SCS programming for chronic back with or without leg pain sufferers without previous back surgery. There is an optional two-way crossover to the other treatment group available for all subjects who remain implanted at the 6 month visit. This scientifically sound study will provide more information on the effectiveness of DTM-SCS programming approach.

B.2. Study Objectives

The **primary objective** of this study is to evaluate the effectiveness of DTM-SCS in reducing back pain as compared to Conventional SCS for the treatment of intractable chronic back pain in subjects without prior history of spine surgery.

The **secondary objectives** of this study are to further demonstrate the effectiveness of the DTM-SCS when compared to Conventional SCS for the treatment of chronic pain of the trunk and limbs. This study will also include the characterization of the safety of DTM-SCS.

B.3. Selection of Study Population

B.3.1. Study Population

The intended study population is individuals suffering from chronic, intractable pain of the trunk and/or limbs who are not considered candidates for spine surgery and are candidates for commercially available SCS device systems.

B.3.2. Inclusion Criteria

In order to participate in the study, a subject must MEET ALL of the following inclusion criteria:

1. Be a candidate for SCS system (trial and implant) per labeled indication (back with or without leg pain)
2. Have been diagnosed with chronic, refractory axial low back pain with a neuropathic component and are not eligible for spine surgery (e.g., lumbar fusion, discectomy, laminectomy, laminotomy) at the time of enrollment
3. Has an average *back* pain intensity ≥ 6.0 cm on the 10.0 cm Visual Analog Scale (VAS) at the time of enrollment

4. Be willing and capable of giving written informed consent to participate in this clinical study based on voluntary agreement after a thorough explanation of the subject's participation has been provided.
5. Be willing and capable of subjective evaluation, read and understand written questionnaires, and read, understand and sign the written informed consent
6. Be 18 years of age or older at the time of enrollment
7. Be on a stable pain medication regime, as determined by the study investigator, for at least 30 days prior to enrolling in this study

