B.7. Study Endpoints

B.7.1. Definition of Analysis Populations

- Modified Intent to Treat (mITT): All successfully randomized subjects who complete the Trial Phase.
- Intent-to-Treat (ITT): All successfully randomized subjects who met all the enrollment criteria.
- Per-Protocol (PP): All subjects who received a permanent device implant and contributed their data to the 3-month endpoint without any major protocol deviations or adverse events (that would render their data unevaluable).

The primary analysis of the primary and secondary endpoints will be performed on the mITT population. Supportive analyses will be performed for the Intent-to-Treat and Per-Protocol population.

For analyses incorporating crossover data (i.e. data gathered in the post 6-month periods), analyses will be based on the mITT population with treatment group defined by the treatment status at the corresponding time point to capture the impact of crossover. Additional sensitivity analyses censoring data post-crossover will be performed to examine the impact of crossover.

B.7.2. Effectiveness Assessment Definitions

- Primary Effectiveness Assessment: For subjects who have a successful Trial Phase and receive a permanent implant, the Primary Efficacy Assessment occurs at the follow up visit 3 months after Device Activation. For subjects who do not have a successful Trial Phase (based on subject's pain score) or subjects who do not want a permanent device implant due to insufficient pain relief (based on subject's discontinuation reason), the Primary Efficacy Assessment occurs at the end of the Trial Phase.

B.7.3. Primary Endpoint

Pain rating on the 10 cm Visual Analog Scale is considered the primary outcome measure. VAS is the most widely used outcome measure in assessing pain due to its documented reliability and validity, ease in administration, and minimal training requirements for the administrator.

- ***Individual Responder:*** A decrease in back pain VAS by at least 50% at 3 months after Permanent Device Activation as compared with Baseline. All subjects must be using the assigned programming parameters. If a subject is switched to a programming parameter that is not considered to be DTM-SCS nor Conventional SCS programming the subject will be counted as a non-responder for the following follow-up visit if one of the two following conditions exist:

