Analysis of both secondary endpoints will be based on a repeated measures approach that accounts for within subject correlation. Treatment group status for the repeated measures models will be based on treatment status at the current time point (i.e. it will be based on treatment status incorporating potential crossover, not necessarily the original randomized assignment).

B.7.5. Additional Data Collection

These following data will be collected:

- Frequency of treatment emergent adverse events
- Comparison of opioid medication usage from baseline at 3, 6, 9 and 12 months after device activation between the two arms
- Comparison of mean change from Baseline in Leg Pain VAS, evaluated at 3, 6, 9 and 12 months after device activation for subjects with baseline leg pain VAS score ≥ 5 between test and control
- Comparison of Leg Pain Treatment Success, measured as at least a 50% reduction in Leg Pain VAS, evaluated at 3, 6, 9, and 12 months after device activation for subjects with baseline leg pain VAS score ≥ 5 between test and control
- Comparison of patient satisfaction between two arms
- Patient Global Impression of Change, evaluated at 3, 6, 9 and 12 months after device activation
- Comparison of Patient Global Impression of Change between two arms

- Comparison of ODI change from baseline at 3, 6, 9 and 12 months after device activation between the two arms
- Comparison of quality of life (QoL) change (from EuroQol EQ-5D-5L) from baseline at 3, 6, 9 and 12 months after device activation between the two arms
- Quality of paresthesia at 3, 6, 9 and 12 months, comparison between test and control
- Percentage of subjects that crossover
- Comparison of mean change from last visit prior to crossover to 12 months visit. This analysis censors data post-crossover.
- Activity level based on Intellis™ adaptive data log (when available)
- Analysis of additional evaluable data items will be based on treatment status at the current time point (i.e. it will be based on treatment status incorporating potential crossover, not necessarily the original randomized assignment).

B.8. Evaluation Criteria

B.8.1. Effectiveness

Results of the tests and standard questionnaires will be recorded in Case Report Forms at Baseline and during follow-up visits. Changes from Baseline will be calculated and compared between the two groups.

Effectiveness will be measured for each subject using the following tests:

- Pain

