 - Visual Analog Scale (VAS, 10 cm) at Baseline, End of Trial Phase, Months 1, 3, 6, 9 and 12
- Disability
 - Oswestry Disability Index Questionnaire
- Quality of Life
 - EuroQol EQ-5D-5L
- Impression of Change in Quality of Life
 - Patient Global Impression of Change
- Satisfaction with Therapy
 - Subject Satisfaction Questionnaire

Study personnel will be appropriately trained for administration of each test.

B.8.2. Definition of Success

The subject's self-reported pain intensity score based on the 10 cm Visual Analog Scale (VAS) is considered the outcome measure for the efficacy component of the primary endpoint. VAS is a widely used outcome measure in assessing pain. It is a reliable and valid

method, which is easy to administer, and requires minimal training for the test administrator. VAS scores will be collected for both back and leg pain.

Study success will be declared if the non-inferiority test for the primary effectiveness endpoint is statistically significant.

There are no additional pre-specified subject or study-level success criteria for secondary and tertiary endpoints.

B.8.3. Safety

Safety will be assessed by characterizing adverse events at all study visits with descriptive statistics.

B.8.3.1 Definitions

An adverse event (AE) is any untoward medical occurrence in a subject associated with the use of the therapy under the study whether or not related to Intellis™ SCS system or the study procedures. An AE is also any event related to any underlying medical condition, present at baseline, which increases in severity or frequency by a clinically meaningful amount during the study as determined by the Investigator.

For all adverse events, the Investigator will provide an assessment of the relationship to the study. If the adverse event is study-related, the following parameters will be assessed: its seriousness, severity, treatment/intervention provided, and resolution.

As the efficacy measures in this study are back and leg pain, back and leg pain do *not* need to be reported as an adverse event unless it meets the definition of a serious adverse event. Investigators may, however, report any other pain-related adverse events during the study.

Pre-existing conditions will not be reported as an adverse event unless there has been a substantial increase in the severity or frequency of the problem, which has not been attributed to its natural history.

A serious adverse event (SAE) is an adverse event that

- Leads to death

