- Leads to serious deterioration in the health of the subject, that either results in
 - a life-threatening illness or injury (life-threatening is defined as at risk of death at the time of the event), or
 - a permanent impairment of a body structure or a body function, or
 - in-patient hospitalization or prolongation of existing hospitalization (in-patient hospitalization is defined as a hospital admission for a period of greater than 24 hours), or
 - medical or surgical intervention to prevent life-threatening illness or injury or permanent impairment to a body structure or a body function,
- Leads to fetal distress, fetal death, or a congenital abnormality or birth defect

Those known adverse events related to the device, procedure or therapy are listed in the section C. (Risk Analysis) of this Investigational Plan.

B.8.3.2 Reporting

All AEs and SAEs will be assessed and captured from enrollment through the completion of the study on the Adverse Event Source Worksheet. AEs and SAEs will be reported as required by the IRB.

All Adverse Events (see list in section C.1.) assessed/determined to be study-related study will document seriousness, severity, treatment/intervention provided, relationship to the device/procedure, and resolution.

Adverse events that are determined to be not study related by the investigator will not be reported in the EDC.

As would be the common practice when using commercial medical devices, device - related AEs may be reported by the site (per their institutional policy) to the Customer Service or Technical Support of Medtronic as specified in the manufacturer's labeling/manuals.

This is a post market, open-label study so Data Monitoring Committee will not be used.

B.9. Data Collection and Analysis

B.9.1. Data Collection

Study data will be collected using a secure Electronic Data Capture system meeting the requirements of 21 CFR part 11. Each data field completed via the EDC system is expected to have a verifiable source document. The clinical site will enter the data from the source documents directly into the EDC system. Subject confidentiality will be maintained, and each subject will be identified only by the assigned study subject number. Subject names will not be published. Data collection is summarized in Table 1.

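### Adverse-event frequency is grouped by current treatment without exposure time or a rule for late implant-related events, so unequal crossover can make raw counts differ at equal risk

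*Combined protocol and SAP*

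**What the plan says.** Section B.2 places safety alongside the secondary objectives: "This study will also include the characterization of the safety of DTM-SCS". The first item in B.7.5 is "Frequency of treatment emergent adverse events". The last entry in that list is the grouping rule "Analysis of additional evaluable data items will be based on treatment status at the current time point", and it adds that this need not be the randomized assignment. B.7.1 sets the same rule for data after month 6: analysis is on the mITT population with "treatment group defined by the treatment status at the corresponding time point to capture the impact of crossover". B.7.1 then adds: "Additional sensitivity analyses censoring data post-crossover will be performed to examine the impact of crossover".

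B.8.3 gives the safety method in one sentence: "Safety will be assessed by characterizing adverse events at all study visits with descriptive statistics". Under B.8.3.2, "All AEs and SAEs will be assessed and captured from enrollment through the completion of the study". For study-related events the investigator also records "relationship to the device/procedure, and resolution".

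B.6.1 offers crossover in both directions to implanted subjects without sufficient relief, to be completed within 30 days of the 6-month visit. The document contains no adverse-event denominator, person-time, safety population or definition of treatment emergence. It also has no rule assigning implant-related events to an arm after a switch.

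**The concern.** Until the 6-month visit both arms are followed on the same schedule, so counts by arm can be compared. After crossover, grouping by current programming moves follow-up time from one column to the other and a subject who switches contributes to both. If more subjects leave Conventional than leave DTM, the DTM column collects more patient-months and, at identical risk, more events. Asymmetry is plausible: crossover is for subjects with insufficient relief, and B.1 reports 3-month responder rates of 80% and 51% in the sponsor's ongoing study of the same two approaches. The plan itself states no expected crossover rate.

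A second effect concerns hardware. Lead migration, erosion or persistent pocket pain (listed in C.1) may start after the switch but come from an implant done under the first assignment. The rule puts such events under the new programming.

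At stake is how the safety tables are read. A difference between columns could reflect time at risk or earlier surgery rather than the programming.

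**Working it through.** The plan gives no adverse-event rate, crossover rate or exposure figure, so there is no figure of its own to reproduce. What follows is expected-value arithmetic.

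**Inputs**
- 12 months of treatment after activation (A.4); crossover between the 6-month visit and 30 days later (B.6.1).
- Assumed: 50 implanted per arm. B.5.5.1 gives 50 per group as randomized and trialed, not implanted.
- Assumed: the hazard is equal in both arms; all subjects complete 12 months; the numbers crossing are as shown below.

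**Patient-months by current programming, crossover at month 6**

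Let c subjects go from Conventional to DTM and d go from DTM to Conventional.
- DTM = 50×6 + (50 − d + c)×6
- Conventional = 50×6 + (50 − c + d)×6

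| Crossing (Conventional, DTM) | DTM | Conventional | Ratio |
|---|---|---|---|
| 40%, 10% (c=20, d=5) | 300 + 65×6 = 690 | 300 + 35×6 = 510 | 1.35 |
| 20%, 10% (c=10, d=5) | 300 + 55×6 = 630 | 300 + 45×6 = 570 | 1.11 |
| Equal numbers | 600 | 600 | 1.00 |

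Under a constant hazard these are also the ratios of expected raw event counts. If more subjects leave DTM than leave Conventional, the ratio falls below 1.

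**Sensitivity to timing (40%, 10%)**
- Crossover at month 7: (350 + 65×5)/(350 + 35×5) = 675/525 = 1.29.
- Adding about 2 months per subject before activation: 790/610 = 1.30 at month 6, 775/625 = 1.24 at month 7.
- The 20%, 10% case becomes 625/575 = 1.09 at month 7, and 730/670 = 1.09 or 725/675 = 1.07 with pre-activation time.

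**Sensitivity to denominator and hazard shape (c=20, d=5, month 6)**

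Two assumed hazards: flat at 0.02 per month (cumulative 0.12 in each half-year), or front-loaded at 0.06 for 3 months and then 0.01 (0.21 in the first half-year, 0.06 in the second). The probability of at least one event is 1 − exp(−cumulative hazard).

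| Measure | Flat: DTM vs Conventional | Front-loaded: DTM vs Conventional |
|---|---|---|
| Expected events | 13.8 vs 10.2 (1.35) | 45×0.27 + 5×0.21 + 20×0.06 = 14.4 vs 30×0.27 + 20×0.21 + 5×0.06 = 12.6 (1.14) |
| Per 100 patient-months, pooled | 2.00 vs 2.00 (1.00) | 14.4/690 = 2.09 vs 12.6/510 = 2.47 (0.84) |
| Percent of ever-treated (70 vs 55) with an event | (45×0.2134 + 25×0.1131)/70 = 17.8% vs (30×0.2134 + 25×0.1131)/55 = 16.8% | (45×0.2366 + 5×0.1894 + 20×0.0582)/70 = 18.2% vs (30×0.2366 + 20×0.1894 + 5×0.0582)/55 = 20.3% |
| Randomized arm, to month 6 | 50×0.12 = 6.0 vs 6.0 | 50×0.21 = 10.5 vs 10.5 |

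The underlying risk is the same throughout, yet the apparent result runs from an excess on DTM to a deficit. Only the comparison by randomized arm to a common cut-off is balanced under both hazards.

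Stopping each subject at the individual crossover date is not fully balanced, because those who stay continue to month 12: 45×12 + 5×6 = 570 against 30×12 + 20×6 = 480 patient-months.

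**What moves to the new arm**

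Only events with onset after crossover do. From the 20 subjects entering DTM that is 20×0.12 = 2.4 of 13.8 expected DTM events (flat) or 20×0.06 = 1.2 of 14.4 (front-loaded), from any cause. Of a switcher's expected events, 0.12/0.24 = 50% (flat) or 0.21/0.27 = 78% (front-loaded) stay with the original arm.

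**The case against.** Four points on the other side carry weight.

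1. The plan says frequency, not raw counts. Read as the percentage of subjects ever treated with each programming, the excess on DTM nearly disappears or reverses. So a reader might infer that the arm receiving more crossovers will necessarily show more events at equal risk; the documents do not support that. What stands is that the denominator is unspecified and its choice can change the direction.

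2. A reader might also infer that events from the original implant are in general charged to the new arm. They are not. Grouping by current status leaves every event with onset before crossover where it was, so early surgical events stay put. The concern is limited to late-onset implant or hardware events.

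3. B.7.1 promises analyses censoring post-crossover data, which comes close to the table needed. But they are supplementary, the sentence does not name adverse events, and B.7.4 and B.7.5 mention censoring only for the responder endpoint and one mean-change item. Censoring also leaves unequal follow-up unless patient-months or a common cut-off are used.

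4. Safety is descriptive, the adverse-event item does not itself ask for a between-arm comparison, and adverse events are absent from the B.9.2.3 list. This limits the consequence. It does not remove the item from the list that the current-status rule governs, and B.7.1 applies the same grouping to post-month-6 data generally.

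**Conclusion.** The point holds in a limited form. The plan groups adverse-event frequency by current treatment and supplies neither exposure time nor a rule for late implant-related events. With unequal crossover, a comparison of columns mixes risk with time at risk.

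For raw counts under a flat hazard, 50 implanted per arm and month-6 crossover, the size is 1.35 at 40% and 10% crossing and 1.11 at 20% and 10%. It is somewhat smaller if crossover is at month 7 or pre-activation time is counted. These crossover rates and hazards are illustrations, not forecasts, and the direction is not fixed. No hypothesis test or success criterion depends on the safety tables. The change is still worth making because characterizing the safety of DTM-SCS is a stated aim, and a better tabulation costs little.

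**What to change.** In B.7.5 and B.8.3:

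1. Make the main adverse-event comparison by randomized arm, from the start of the Trial Phase (trial lead placement) to crossover or to a common month-6 cut-off. The common cut-off is the cleaner choice; if individual crossover dates are used, give patient-months alongside.
2. Tabulate post-crossover events separately by current programming, as events per 100 patient-months. Do not pool them with pre-crossover time: under front-loaded risk the pooled rate is itself misleading (0.84 in the example above).
3. Show procedure- and hardware-related events from the original implant under the randomized arm, using the device/procedure relationship already recorded for study-related events.

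Define treatment emergence and the safety population in the same place.

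The cost is SAP wording and two or three extra descriptive tables. The crossover date must be recorded, but the current-status rule already depends on it. No visit or procedure is added.

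### Adverse events judged unrelated, including serious ones, stay out of the EDC, so a safety summary drawn from it would be narrower than its label

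*Combined protocol and SAP*

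**What the plan says.** **The outputs.** B.2 includes characterizing the safety of DTM-SCS among the study's aims. B.8.3 says how: "Safety will be assessed by characterizing adverse events at all study visits with descriptive statistics". B.7.5 lists "Frequency of treatment emergent adverse events" among the additional data. Neither carries a relatedness limit.

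**The definition.** B.8.3.1 defines an adverse event as an untoward occurrence tied to use of the study therapy, and adds that it counts irrespective of relationship to the Intellis system or the study procedures. An SAE is defined as a kind of adverse event. On attribution: "For all adverse events, the Investigator will provide an assessment of the relationship to the study".

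**The data flow.** B.8.3.2 begins with full capture at source: "All AEs and SAEs will be assessed and captured from enrollment through the completion of the study on the Adverse Event Source Worksheet". It then excludes: "Adverse events that are determined to be not study related by the investigator will not be reported in the EDC". B.9.1 names the database: "Study data will be collected using a secure Electronic Data Capture system meeting the requirements of 21 CFR part 11".

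**Seriousness.** B.8.3.1 says "If the adverse event is study-related, the following parameters will be assessed: its seriousness, severity", followed by treatment given and resolution. B.8.3.2 asks for similar detail on events "assessed/determined to be study-related study will document seriousness, severity, treatment/intervention provided, relationship to the device/procedure, and resolution". E.3 makes the investigator responsible for judging the relationship and the seriousness of adverse events, without confining the seriousness judgement to related ones.

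**The concern.** The plan promises a summary of adverse events and then fills its database with a subset of them. The filter is one judgement, relatedness, made by an investigator who knows the treatment group, since B.5.4 says site personnel cannot be blinded.

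Safety has no hypothesis and no success criterion, so the descriptive summary is the whole safety result. A reader of a treatment-emergent table expects all events arising on treatment, with the related ones as a subset. The table this plan would produce is the subset alone. SAEs are the more important omission: a reader would normally want to see every one, precisely so as not to depend on the attribution.

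**Working it through.** No figure in the plan can be reproduced here, so the check sets the sections side by side.

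1. **Does the plan expect unrelated adverse events?** Yes. B.8.3.1 requires a relationship assessment for every event, and the exclusion sentence in B.8.3.2 would have nothing to act on if every adverse event were study-related by definition.

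2. **Does the exclusion cover SAEs?** Yes. SAEs are a kind of adverse event in B.8.3.1, and B.8.3.2 states no exception. The 48-hour report to the sponsor in E.3 is confined to study-related SAEs, so it does not bring unrelated ones in.

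3. **Do the outputs carry the same limit?** No. The B.7.5 item and the B.8.3 sentence are both unrestricted.

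4. **Is another data source named for the safety summary?** No. The other places an unrelated event can be recorded are:
   - the Adverse Event Source Worksheet, which keeps the event at the site;
   - IRB reporting, which B.8.3.2 sets by IRB requirements without a relatedness limit;
   - the unscheduled-visit eCRF (B.6.10), which documents the visit;
   - the Study Termination eCRF (B.6.19), which gives the reason for withdrawal, and the listed reasons include death and adverse events.

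   None is described as feeding the safety summary. Source verification (E.1.2) checks what has been entered in the EDC, and data review (E.2) looks for potential study-related events. Neither is said to bring in events judged unrelated.

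5. **What would the table contain?** Let R be the number of events judged study-related and U the number judged unrelated. The full count is R + U. A table drawn from the EDC shows R, and its count of unrelated events is 0 by design. The missing share is U / (R + U). The plan gives neither R nor U, nor any rate from which to derive them, so the share could lie anywhere from 0 upward and no estimate is offered.

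6. **Would unrelated events be classified as serious at source?** This is unclear. B.8.3.1 and the second paragraph of B.8.3.2 specify seriousness for study-related events, while E.3 has no such limit. Sorting events into AEs and SAEs on the worksheet presupposes the judgement. So does the B.8.3.1 rule under which back or leg pain need be reported only if it meets the SAE definition. The wording should be made consistent.

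**The case against.** The strongest reply is that this is a deliberate post-market choice. Both arms use one commercially available system within its labeling, related events are a reasonable focus for characterizing the safety of a programming approach, and the exclusion sits in a subsection of the safety section itself. That stands as a defence of not entering every minor unrelated event. It does not defend a label that hides the limit, or the omission of unrelated SAEs.

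A second reply is that the definition in B.8.3.1, by tying an adverse event to use of the therapy, already implies relatedness. The wording is ambiguous, but the same sentence includes events not related to the system or procedures, and the plan goes on to provide for events judged unrelated.

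Third, the events are not lost: worksheet, IRB reporting and termination form all keep something. That is right, and it lowers the stakes. It does not put the events into the summary.

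A reader might also infer more than the documents support:

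- **That unblinded attribution biases the comparison of arms.** The documents give no attribution rate by arm and no sign that attribution would differ. The B.7.5 item is not even worded as a comparison between arms.
- **That unrelated deaths go unrecorded.** Death is a listed withdrawal reason, and a termination eCRF is completed.
- **That seriousness is never judged for unrelated events.** B.8.3.1 and B.8.3.2 require it for related events but do not forbid it for others, and E.3 assigns it generally.

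**Conclusion.** The point holds as a mismatch between the safety outputs and the data that the plan sends to the database. Followed as written, and if the summary is produced from the EDC, the plan yields investigator-attributed study-related events under a treatment-emergent label, with no unrelated SAEs.

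The conclusion rests on one assumption: that the safety summary is drawn from the EDC. The plan does not say so outright, but it names no other source.

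The size cannot be computed. The primary non-inferiority test is unaffected, and nothing here shows distortion between arms. This is an inexpensive improvement to the study's only safety result. It is not a flaw in the efficacy design.

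**What to change.** 1. In B.8.3.2, amend the exclusion sentence so that all SAEs, including deaths, are entered in the EDC whatever their relationship, with relatedness as a field. Summarize them descriptively.
2. In B.7.5 and B.8.3, label the non-serious output *study-related adverse events as judged by the investigator*, unless all adverse events are entered.
3. In B.8.3.1 and B.8.3.2, state that seriousness is assessed for every adverse event, in line with E.3.

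**Cost.** Sites enter, and monitors check, the additional SAEs, which are already on the worksheet. Their number is expected to be limited but cannot be computed from the plan. The eCRF completion guideline needs an edit. The seriousness judgement adds little, because E.3 already assigns it to the investigator.

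Entering all unrelated non-serious events would remove the need for the restricted label, but it is optional. In a post-market study of a commercial device the added data entry is a fair reason to decline it, provided the label states the limit.
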